APPENDIX 5: DOSE MODIFICATION AND TOXICITY MANAGEMENT FOR OLAPARIB

Any toxicity observed during the course of the study could be managed by interruption of the dose of study treatment or dose reductions. Repeat dose interruptions are allowed as required, for a maximum of 4 weeks on each occasion. If the interruption is any longer, the study team must be informed. Study treatment can be dose reduced to 250 mg twice daily as a first step and to 200 mg twice daily as a second step. If the reduced dose of 200 mg twice daily is not tolerable, no further dose reduction is allowed and study treatment should be discontinued. Once dose is reduced, escalation is not permitted.

RENAL IMPAIRMENT

If after study entry and while still on study therapy, a patient's estimated CrCl falls below the threshold for study inclusion (≥ 51 ml/min), retesting should be performed promptly.

A dose reduction is recommended for patients who develop moderate renal impairment (calculated creatinine clearance by Cockcroft-Gault equation of between 31 and 50 ml/min) for

any reason during the study: the dose of olaparib should be reduced to 200mg twice daily.

Because the CrCl determination is only an estimate of renal function, in instances where the CrCl falls to between 31 and 50 mL/min, the investigator should use his or her discretion in determining whether a dose change or discontinuation of therapy is warranted.

Olaparib has not been studied in patients with severe renal impairment (creatinine clearance ≤ 30 mL/min) or end-stage renal disease; if patients develop severe impairment or end stage disease is it recommended that olaparib be discontinued

MANAGEMENT OF HEMATOLOGICAL TOXICITY

Management of anemia

Table 5: Management of anemia

Anemia	Management/Next Dose for olaparib
\leq Grade 1 Grade 2	Give appropriate supportive treatment and investigate causality. Investigator judgement to continue olaparib with supportive treatment (eg transfusion) or interrupt dose for a maximum of 4 weeks. If repeat Hb < 10 but ≥ 8 g/dl , dose interrupt (for max of 4 weeks) until Hb ≥ 10 g/dl and upon recovery dose reduction to 250 mg twice daily as a first step and to 200 mg twice daily as a second step may be considered.
Grade 3 Grade 4	Give appropriate supportive treatment (e.g. transfusion) and investigate causality. Interrupt olaparib for a maximum of 4 weeks. until improved to Hb ≥ 10 g/dl. Upon recovery dose reduce to 250 mg twice daily as a first step and to 200 mg twice daily as a second step in the case of repeat Hb decrease.

*Patients requiring a delay of >4 weeks should go off protocol therapy. The Study Principal Investigator should be consulted for possible resumption of treatment at a lower dose for patients who showed disease response.

**Patients requiring > two dose reductions should go off protocol therapy.

Management of neutropenia, leukopenia, and thrombocytopenia

Table 6: Management of neutropenia, leukopenia and thrombocytopenia

Neutropenia/leukopenia/thrombocytopenia	Management/Next Dose for olaparib
≤ Grade 1 Grade 2	Investigator judgement to continue treatment or if dose interruption, this should be for a maximum of 4 weeks; appropriate supportive treatment and causality investigation
Grade 3 Grade 4	Dose interruption until recovered to CTCAE gr 1 or better for a maximum of 4 weeks. If repeat CTCAE grade 3-4 occurrence, dose reduce olaparib to 250 mg twice daily as a first step and 200 mg twice daily as a second step

*Patients requiring a delay of >4 weeks should go off protocol therapy. The Study Principal Investigator should be consulted for possible resumption of treatment at a lower dose for patients who showed disease response.

**Patients requiring > two dose reductions should go off protocol therapy.

Adverse event of neutropenia and leukopenia should be managed as deemed appropriate by the investigator with close follow up and interruption of study drug if CTCAE grade 3 or worse neutropenia occurs.

Primary prophylaxis with Granulocyte colony-stimulating factor (G-CSF) is not recommended, however, if a patient develops febrile neutropenia, study treatment should be stopped and appropriate management including G-CSF should be given according to local hospital guidelines. Please note that G-CSF should not be used within at least 24 h (7 days for pegylated G-CSF) of the last dose of study treatment unless necessary.

Platelet transfusions, if indicated, should be done according to local hospital guidelines. For cases where patients develop prolonged hematological toxicity (≥2 week interruption/delay in study treatment due to CTCAE grade 3 or worse), refer to Section 5.2.2.3.3

Management of prolonged hematological toxicities while on study treatment

If a patient develops prolonged hematological toxicity such as:

- ≥2 week interruption/delay in study treatment due to CTCAE grade 3 or worse anemia and/or development of blood transfusion dependence
- ≥2 week interruption/delay in study treatment due to CTCAE grade 3 or worse neutropenia (ANC < 1 x 10⁹/L)

- ≥ 2 week interruption/delay in study treatment due to CTCAE grade 3 or worse thrombocytopenia and/or development of platelet transfusion dependence (Platelets $< 50 \times 10^9/L$)

Check weekly differential blood counts including reticulocytes and peripheral blood smear. If any blood parameters remain clinically abnormal after 4 weeks of dose interruption, the patient should be referred to hematologist for further investigations. Bone marrow analysis and/or blood cytogenetic analysis should be considered at this stage according to standard hematological practice. Study treatment should be discontinued if blood counts do not recover to CTCAE gr 1 or better within 4 weeks of dose interruption.

Development of a confirmed myelodysplastic syndrome or other clonal blood disorder should be reported as an SAE and full reports must be provided by the investigator to NCI CTEP. Olaparib treatment should be discontinued if patient's diagnosis of MDS and/or AML is confirmed.

MANAGEMENT OF NON-HEMATOLOGICAL TOXICITY

Management of new or worsening pulmonary symptoms

If new or worsening pulmonary symptoms (e.g., dyspnea) or radiological abnormalities occur in the absence of a clear diagnosis, an interruption in study treatment dosing is recommended and further diagnostic workup (including a high resolution CT scan) should be performed to exclude pneumonitis.

Following investigation, if no evidence of abnormality is observed on CT imaging and symptoms resolve, then study treatment can be restarted, if deemed appropriate by the investigator. If significant pulmonary abnormalities are identified, these need to be discussed with the Principal Investigator.

Management of nausea, vomiting and diarrhea

Events of nausea and vomiting are known to be associated with olaparib treatment. In study D0810C00019 nausea was reported in 71% of the olaparib treated patients and 36% in the placebo treated patients and vomiting was reported in 34% of the olaparib treated patients and 14% in the placebo treated patients. These events are generally mild to moderate (CTCAE grade 1 or 2) severity, intermittent and manageable on continued treatment. The first onset generally occurs in the first month of treatment for nausea and within the first 6 months of treatment for vomiting. For nausea, the incidence generally plateaus at around 9 months, and for vomiting at around 6 to 7 months.

No routine prophylactic anti-emetic treatment is required at the start of study treatment, however, patients should receive appropriate anti-emetic treatment at the first onset of nausea or vomiting and as required thereafter, in accordance with local treatment practice guidelines. Alternatively, olaparib tablets can be taken with a light meal/snack (ie 2 pieces of toast or a couple of biscuits).

As per international guidance on anti-emetic use in cancer patients (ESMO, NCCN) generally a single agent antiemetic should be considered eg dopamine receptor antagonist, antihistamines or dexamethasone.

Table 7: Management of nausea

Nausea	Management/Next Dose for olaparib
≤ Grade 1	No change in dose
Grade 2	Hold until ≤ Grade 1. Resume at same dose level
Grade 3	Hold* until <Grade 2. Resume at one dose level lower, if indicated.**
Grade 4	Off protocol therapy

*Patients requiring a delay of >4 weeks should go off protocol therapy. The Study Principal Investigator should be consulted for possible resumption of treatment at a lower dose for patients who showed disease response.

**Patients requiring > two dose reductions should go off protocol therapy.

Table 8: Management of vomiting

Vomiting	Management/Next Dose for olaparib
≤ Grade 1	No change in dose
Grade 2	Hold until ≤ Grade 1. Resume at same dose level
Grade 3	Hold* until <Grade 2. Resume at one dose level lower, if indicated.**
Grade 4	Off protocol therapy

*Patients requiring a delay of >4 weeks should go off protocol therapy. The Study Principal Investigator should be consulted for possible resumption of treatment at a lower dose for patients who showed disease response.

**Patients requiring > two dose reductions should go off protocol therapy.

Table 9: Management of diarrhea

Diarrhea	Management/Next Dose for olaparib
≤ Grade 1	No change in dose
Grade 2	Hold until ≤ Grade 1. Resume at same dose level

Grade 3	Hold* until <Grade 2. Resume at one dose level lower, if indicated.**
Grade 4	Off protocol therapy

*Patients requiring a delay of >4 weeks should go off protocol therapy. The Study Principal Investigator should be consulted for possible resumption of treatment at a lower dose for patients who showed disease response.

**Patients requiring > two dose reductions should go off protocol therapy.

Recommended management: Loperamide antidiarrheal therapy

Dosage schedule: 4 mg at first onset, followed by 2 mg with each loose motion until diarrhea-free for 12 hours (maximum dosage: 16 mg/24 hours)

Adjunct anti-diarrheal therapy is permitted and should be recorded when used.

Interruptions for intercurrent non-toxicity related events

Study treatment dose interruption for conditions other than toxicity resolution should be kept as short as possible. If a patient cannot restart study treatment within 4 weeks for resolution of intercurrent conditions not related to disease progression or toxicity, the case should be discussed with Study Principal Investigator.

All dose reductions and interruptions (including any missed doses), and the reasons for the reductions/interruptions are to be recorded in the eCRF.

Study treatment should be stopped at least 3 days prior to planned surgery. After surgery study treatment can be restarted when the wound has healed. No stoppage of study treatment is required for any needle biopsy procedure.

Study treatment should be discontinued for a minimum of 3 days before a patient undergoes radiation treatment.

Because the AEs related to olaparib may include asthenia, fatigue and dizziness, patients should be advised to use caution while driving or using machinery if these symptoms occur.

APPENDIX 6: DOSE MODIFICATION AND TOXICITY MANAGEMENT FOR IMMUNE-RELATED AES ASSOCIATED WITH PEMBROLIZUMAB

AEs associated with pembrolizumab exposure, including coadministration with additional compounds may represent an immunologic etiology. These immune-related AEs (irAEs) may occur shortly after the first dose or several months after the last dose of pembrolizumab treatment and may affect more than one body system simultaneously. Therefore, early recognition and initiation of treatment is critical to reduce complications. Based on existing clinical study data, most irAEs were reversible and could be managed with interruptions of pembrolizumab, administration of corticosteroids and/or other supportive care.

For suspected irAEs, ensure adequate evaluation to confirm etiology or exclude other causes.

Additional procedures or tests such as bronchoscopy, endoscopy, skin biopsy may be included as part of the evaluation. Based on the severity of irAEs, withhold or permanently discontinue pembrolizumab and administer corticosteroids. Dose modification and toxicity management guidelines for irAEs associated with pembrolizumab are provided in Table 10.

Table 10: Dose modification and toxicity management guidelines for immune-related AEs associated with pembrolizumab

General instructions:				

 1. Corticosteroid taper should be initiated upon AE improving to Grade 1 or less and continue to taper over at least 4 weeks. 2. For situations where pembrolizumab has been withheld, pembrolizumab can be resumed after AE has been reduced to Grade 1 or 0 and corticosteroid has been tapered. Pembrolizumab should be permanently discontinued if AE does not resolve within 12 weeks of last dose or corticosteroids cannot be reduced to ≤ 10 mg prednisone or equivalent per day within 12 weeks. 3. For severe and life-threatening irAEs, IV corticosteroid should be initiated first followed by oral steroid. Other immunosuppressive treatment should be initiated if irAEs cannot be controlled by corticosteroids. 				
Immune-related AEs	Toxicity grade or conditions (CTCAEv5.0)	Action taken to pembrolizumab	irAE management with corticosteroid and/or other therapies	Monitor and follow-up
Pneumonitis	Grade 2	Withhold	
 • Administer corticosteroids (initial dose of 1-2 mg/kg prednisone or equivalent) followed by taper 	
 • Monitor participants for signs and symptoms of pneumonitis • Evaluate participants with suspected pneumonitis with radiographic imaging and initiate corticosteroid treatment • Add prophylactic antibiotics for opportunistic infections
	Grade 3 or 4, or recurrent Grade 2	Permanently discontinue		
Diarrhea / Colitis	Grade 2 or 3	Withhold	
 • Administer corticosteroids (initial dose of 1-2 mg/kg prednisone or equivalent) followed by taper 	
 • Monitor participants for signs and symptoms of enterocolitis (ie, diarrhea, abdominal pain, blood or mucus in stool with or without fever) and of bowel perforation (ie, peritoneal signs and ileus). • Participants with \geq Grade 2 diarrhea suspecting colitis should consider GI consultation and performing endoscopy to rule out colitis. • Participants with diarrhea/colitis should be advised to drink liberal quantities of clear fluids. If sufficient oral fluid intake is not feasible, fluid and electrolytes should be substituted via IV infusion.
	Grade 4	Permanently discontinue		
AST / ALT elevation or	Grade 2	Withhold	
 • Administer corticosteroids (initial dose of 0.5- 1 mg/kg prednisone or equivalent) followed by taper 	
 • Monitor with liver function tests (consider weekly or more frequently until liver

Increased bilirubin	Grade 3 or 4	Permanently discontinue	
 Administer corticosteroids (initial dose of 1-2 mg/kg prednisone or equivalent) followed by taper 	enzyme value returned to baseline or is stable
Type 1 diabetes mellitus (T1DM) or Hyperglycemia	Newly onset T1DM or Grade 3 or 4 hyperglycemia associated with evidence of β -cell failure	Withhold	
 Initiate insulin replacement therapy for participants with T1DM Administer anti-hyperglycemic in participants with hyperglycemia 	
 Monitor participants for hyperglycemia or other signs and symptoms of diabetes.
Hypophysitis	Grade 2	Withhold	
 Administer corticosteroids and initiate hormonal replacements as clinically indicated. 	
 Monitor for signs and symptoms of hypophysitis (including hypopituitarism and adrenal insufficiency)
	Grade 3 or 4	Withhold or permanently discontinue ¹		
Hyperthyroidism	Grade 2	Continue	
 Treat with non-selective beta-blockers (eg, propranolol) or thionamides as appropriate 	
 Monitor for signs and symptoms of thyroid disorders.
	Grade 3 or 4	Withhold or permanently discontinue ¹		
Hypothyroidism	Grade 2	Continue	
 Initiate thyroid replacement hormones (eg, levothyroxine or liothyronine) per standard of care 	
 Monitor for signs and symptoms of thyroid disorders.
	Grade 3 or 4	Withhold or permanently discontinue		
Nephritis and Renal dysfunction	Grade 2	Withhold	
 Administer corticosteroids (prednisone 1-2 mg/kg or equivalent) followed by taper. 	
 Monitor changes of renal function
Myocarditis	Asymptomatic cardiac enzyme elevation with clinical suspicion of	Withhold	
 Based on severity of AE administer corticosteroids 	
 Ensure adequate evaluation to confirm etiology and/or exclude other causes

	myocarditis (which was previously myocarditis Grade 1 using CTCAE v4.0)			
	Grade 2, 3 or 4	Permanently discontinue		
	Intolerable/persistent Grade 2	Withhold	
 Based on type and severity of AE administer corticosteroids 	
 Ensure adequate evaluation to confirm etiology and/or exclude other causes
All other immune-related AEs	Grade 3	Withhold or discontinue based on the type of event. Events that require discontinuation include and not limited to: Guillain-Barre Syndrome, encephalitis		
	Grade 4 or recurrent Grade 3	Permanently discontinue		

1. Withhold or permanently discontinue pembrolizumab is at the discretion of the investigator or treating physician.

NOTE:

For participants with Grade 3 or 4 immune-related endocrinopathy where withhold of pembrolizumab is required, pembrolizumab may be resumed when AE resolves to \leq Grade 2 and is controlled with hormonal replacement therapy or achieved metabolic control (in case of T1DM).

Dose modification and toxicity management of infusion-reactions related to pembrolizumab

Pembrolizumab may cause severe or life threatening infusion-reactions including severe hypersensitivity or anaphylaxis. Signs and symptoms usually develop during or shortly after drug infusion and generally resolve completely within 24 hours of completion of infusion. Dose modification and toxicity management guidelines on pembrolizumab associated infusion reaction are provided in Table 11.

Table 11: Pembrolizumab Infusion Reaction Dose modification and Treatment Guidelines

NCI CTCAE Grade	Treatment	Premedication at Subsequent Dosing
Grade 1 Mild reaction; infusion interruption not indicated; intervention not indicated	Increase monitoring of vital signs as medically indicated until the participant is deemed medically stable in the opinion of the investigator.	None
Grade 2 Requires therapy or infusion interruption but responds promptly to symptomatic treatment (e.g., antihistamines, NSAIDs, narcotics, IV fluids); prophylactic medications indicated for ≤24 hrs	
Stop Infusion. Additional appropriate medical therapy may include but is not limited to: IV fluids Antihistamines NSAIDs Acetaminophen Narcotics
 
Increase monitoring of vital signs as medically indicated until the participant is deemed medically stable in the opinion of the investigator. If symptoms resolve within 1 hour of stopping drug infusion, the infusion may be restarted at 50% of the original infusion rate (e.g. from 100 mL/hr to 50 mL/hr). Otherwise dosing will be held until symptoms resolve and the participant should be premedicated for the next scheduled dose.
 
Participants who develop Grade 2 toxicity despite adequate premedication should be permanently discontinued from further study drug treatment
	Participant may be premedicated 1.5h (± 30 minutes) prior to infusion with: Diphenhydramine 50 mg po (or equivalent dose of antihistamine). Acetaminophen 500-1000 mg po (or equivalent dose of analgesic).


Grades 3 or 4
 
Grade 3: Prolonged (i.e., not rapidly responsive to symptomatic medication and/or brief interruption of infusion); recurrence of symptoms following initial improvement; hospitalization indicated for other clinical sequelae (e.g., renal impairment, pulmonary infiltrates)
 
Grade 4: Life-threatening; pressor or ventilatory support indicated
	
Stop Infusion.
 
Additional appropriate medical therapy may include but is not limited to: Epinephrine** IV fluids Antihistamines NSAIDs Acetaminophen Narcotics Oxygen Pressors Corticosteroids
 
Increase monitoring of vital signs as medically indicated until the participant is deemed medically stable in the opinion of the investigator. Hospitalization may be indicated.
 
**In cases of anaphylaxis, epinephrine should be used immediately.
 
Participant is permanently discontinued from further study drug treatment.
	
No subsequent dosing

Appropriate resuscitation equipment should be available at the bedside and a physician readily available during the period of drug administration. For further information, please refer to the Common Terminology Criteria for Adverse Events v5.0 (CTCAE) at http://ctep.cancer.gov
		

Other allowed dose interruption for pembrolizumab

Pembrolizumab may be interrupted for situations other than treatment-related AEs such as medical / surgical events or logistical reasons not related to study therapy. Participants should be placed back on study therapy within 3 weeks of the scheduled interruption, unless otherwise discussed with the Sponsor-Investigator. The reason for interruption should be documented in the patient's study record.

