7.2 PARTICIPANT DISCONTINUATION/WITHDRAWAL FROM STUDY

Participants are free to withdraw from participation in the study at any time upon request.

In addition, the investigator has the right to withdraw a patient from the study at any time should any untoward effect occur. In addition, a participant may be discontinued from study treatment by the investigator or the Sponsor if study treatment is inappropriate, the trial plan is violated, or for administrative and/or other safety reasons. Specific details regarding procedures to be performed at study treatment discontinuation are provided in Section 8.1.4.1.

A participant must be discontinued from study treatment but continue to be monitored in the study and moved to survival follow-up for any of the following reasons:

- The participant or participant's legally acceptable representative requests to discontinue study treatment
- Confirmed radiographic disease progression outlined in Section 8.1.2.6
- Any progression or recurrence of any malignancy, or any occurrence of another malignancy that requires active treatment

Note: Participants with basal cell carcinoma of the skin, squamous cell carcinoma of the skin, or carcinoma in situ (excluding carcinoma in situ of the bladder) who have undergone potentially curative resection do not have to discontinue study intervention.

- Unacceptable adverse experiences as described in Appendix 5 and Appendix 6.
- The participant has a medical condition or personal circumstance which, in the opinion of the treating investigator and/or sponsor, placed the participant at unnecessary risk from continued administration of study treatment.
- Sponsor-Investigator determines it is in the best interest of the patient
- Patient non-compliance with the study treatment or procedure as determined by the treating investigator
- The participant has a confirmed positive serum pregnancy test
- Recurrent Grade 2 pneumonitis
- Discontinuation of treatment may be considered for participants who have attained a confirmed complete response (CR) and have been treated for at least 8 cycles (at least 24 weeks), receiving 2 cycles of the combination including 2 doses of pembrolizumab and at least 80% of the planned doses of olaparib and pembrolizumab beyond the date when the initial CR was declared. These participants may be eligible for second course treatment described in Appendix 7.
- Administrative reasons

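### Appendix 5 gives conflicting instructions for a responding patient whose blood counts have not recovered after a 4-week olaparib interruption

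*Combined protocol and SAP*

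**What the plan says.** Appendix 5 deals with long olaparib interruptions in several places.

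- **General text, any toxicity.** "Repeat dose interruptions are allowed as required, for a maximum of 4 weeks on each occasion". The next sentence is "If the interruption is any longer, the study team must be informed". It does not mention stopping and does not refer to the tables.
- **Footnote to Tables 5 and 6 (anemia; neutropenia, leukopenia and thrombocytopenia).** "Patients requiring a delay of >4 weeks should go off protocol therapy". It continues: "The Study Principal Investigator should be consulted for possible resumption of treatment at a lower dose for patients who showed disease response". The same footnote is repeated under Tables 7 to 9 (nausea, vomiting, diarrhea).
- **Paragraph on prolonged hematological toxicity.** "Study treatment should be discontinued if blood counts do not recover to CTCAE gr 1 or better within 4 weeks of dose interruption". It contains no exception for responders.
- **Pointer after Table 6.** For interruptions of 2 weeks or more due to grade 3 or worse hematological toxicity, the reader is told to "refer to Section 5.2.2.3.3".
- **Interruptions not caused by toxicity.** These have their own sentence, beginning "If a patient cannot restart study treatment within 4 weeks for resolution of intercurrent conditions not related to disease progression or toxicity", which asks for discussion with the Study Principal Investigator. Its scope is different and it is not part of the conflict.

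Section 7.2 lists among the reasons for which a participant must be discontinued: "Unacceptable adverse experiences as described in Appendix 5 and Appendix 6".

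**The concern.** The footnote and the prolonged-toxicity paragraph both cover a patient whose counts have not recovered after 4 weeks off olaparib. One leaves a route back to treatment if the patient has responded; the other does not. Two sites could treat identical patients differently, and each could cite Appendix 5.

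This is a discontinuation rule for toxicity, and Section 7.2 gives it mandatory force without restating it. If Appendix 5 has two answers, so does Section 7.2. Section 10.1.9 counts any noncompliance with the protocol as a deviation to be reported, so the same action could be logged as a deviation or as compliance. For the patients concerned, the choice of text also affects time on olaparib, and hence the exposure summary in Section 9.4.5 and possibly their PFS and duration of response.

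**Working it through.** No calculation applies, because the plan states no figure on this point. The check is to take each type of patient with a toxicity-related hold beyond 4 weeks and read off what each passage requires.

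1. **Responder; grade 3 or 4 neutropenia, thrombocytopenia or anemia; counts not at grade 1 by week 4.** General text: inform the study team. Footnote to Tables 5 and 6: off protocol therapy, with resumption at a lower dose possible after consultation. Prolonged-toxicity paragraph: discontinue, no exception. The last two give different outcomes.
2. **Non-responder, same toxicity.** The footnote and the paragraph both stop treatment. The general text adds a duty to inform. All three can be followed together.
3. **Grade 3 nausea, vomiting or diarrhea held beyond 4 weeks.** The footnote to Tables 7 to 9 applies, with its responder exception. The prolonged-toxicity paragraph concerns blood counts only and does not apply. The general text states a weaker consequence and does not point to the footnote.
4. **A toxicity with no table of its own.** Within these passages only the general text speaks: a 4-week maximum, and notification if it is exceeded. No consequence for treatment is given.

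Next, is there anything that settles case 1? No passage says which text prevails. The pointer after Table 6 might have done so, but Section 5.2 of this protocol is the list of exclusion criteria and has no subsection 5.2.2.3.3. Section 7.2 refers back to Appendix 5 as a whole, so it carries the ambiguity forward.

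Last, what does the conflict reach in the analysis? Section 9.3 includes all eligible patients who received any of the target treatment, whether or not they later stop. The denominator for the primary ORR is therefore the same under either text.

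**The case against.** The strongest reply is that the passages can mostly be read together.

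- **The general text is compatible with stopping.** It sets a 4-week maximum, and informing the team does not prevent discontinuation. This stands. A reader might infer three mutually exclusive rules, but the general text never says a patient may stay on hold past week 4. Its fault is that it names a lesser consequence and does not refer to the stopping rules.
- **The pointer may be meant for the prolonged-toxicity paragraph.** Its subject matches that paragraph's heading, so this is a fair guess at intent. It partly stands. But the cited section does not exist, and a pointer to further guidance does not say that the responder exception in the footnote is switched off.
- **The two texts may be sequential: stop first, then consider resumption.** The footnote itself works that way. The paragraph, however, mentions no resumption, and Section 7.2 moves a patient discontinued under Appendix 5 to survival follow-up rather than to a hold.
- **Safeguards remain.** In prolonged hematological toxicity the appendix requires weekly counts, hematology referral if values stay abnormal after 4 weeks, and an end to olaparib if MDS or AML is confirmed. Resumption under the footnote needs consultation and a lower dose. This stands, and it argues against presenting the conflict as an uncontrolled marrow risk.

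The asterisk tying the footnote to particular rows is visible in Tables 7 to 9 but not in Tables 5 and 6. That may be a loss in the PDF text, so nothing here rests on it.

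**Conclusion.** The contradiction is real but narrow. For a patient who has responded and whose counts have not reached grade 1 or better within 4 weeks of interruption, Appendix 5 both leaves resumption open and directs discontinuation without exception. Section 7.2 takes over that ambiguity as a mandatory criterion. For non-responders the footnote and the paragraph agree. For gastrointestinal toxicity the weakness is only the missing link between the general text and the footnotes.

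Three stronger inferences are not supported:

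- **A count of affected patients.** Assuming that 10 to 20% of the 26 patients have a hold beyond 4 weeks gives 26 × 0.10 = 2.6 to 26 × 0.20 = 5.2. Applying the Section 9.2 response rates gives 2.6 × 0.25 = 0.65 to 5.2 × 0.45 = 2.34 responders. The documents give no rate of such holds. The sum also treats every hold as hematological and unrecovered, and response as already established, although the first on-study scan is at 9 weeks (Section 8.1.2.6.1). The number cannot be calculated.
- **Duration of response differing by response status.** Section 9.3 restricts that analysis to responders, so no such comparison exists.
- **Damage to the primary test.** The denominator is fixed by Section 9.3, and the exception concerns patients who have already shown a response.

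The point rests on the text alone. It warrants correction because it concerns a safety discontinuation rule, not because it threatens the primary result.

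**What to change.** Reconcile the Appendix 5 passages on toxicity-related interruptions beyond 4 weeks into one consistent rule: the general text, the footnotes to Tables 5 to 9, and the prolonged hematological toxicity paragraph. State in that rule whether any exception exists and to whom it applies, so that it reads the same wherever it is invoked. Cite it from the general text and from each table footnote, and replace the reference to Section 5.2.2.3.3 with the correct location. Section 7.2 can then stay as written, because its reference to Appendix 5 will have one meaning. The clinical team decides what the rule should be; this review takes no view on that.

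The cost is amendment wording in one appendix, with no added patients, visits or data and no change to the sample size or the primary analysis.
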